7.3.3 Safety analyses

Safety will be assessed for the endpoints listed in [Section 5.2.1](#). All treated subjects (i.e., all subjects who received at least one dose of study drug), will be included in the safety analysis. Safety analyses will be descriptive and will be based on BI standards. No hypothesis testing is planned.

The analyses will be done by ‘treatment at onset’.

Treatments will be compared in a descriptive way. Tabulations of frequencies/proportions will be used for the evaluation of categorical (qualitative) data, and tabulations of descriptive statistics will be used to analyse continuous (quantitative) data.

Measurements (such as ECG, vital signs, or laboratory parameters) or AEs will be assigned to treatments (see [Section 4.1](#)) based on the actual treatment at the planned time of the measurement or on the recorded time of AE onset (concept of ‘treatment emergent AEs’).

Proprietary confidential information © 2016 Boehringer Ingelheim International GmbH or one or more of its affiliated companies

Therefore, all AEs which will occur throughout the treatment phase and the preliminary REP will be considered as 'on treatment'. Events which occurred after the preliminary REP will be considered as 'follow-up' events (refer to [Section 5.2.2.2](#)).

These assignments, including the corresponding time intervals, will be defined in detail in the TSAP.

Adverse events will be coded using the Medical Dictionary for Regulatory Activities (MedDRA). Frequency, severity and causal relationship of AEs will be tabulated by treatment, primary system organ class and preferred term. SAEs and other significant AEs (according to ICH E3), and AESIs will be listed separately (see [Section 5.2.2.1](#)).

Laboratory data will be compared to their reference ranges. Values outside the reference range as well as values defined as clinically relevant will be highlighted in the listings. Additionally, differences from baseline will be evaluated.

Vital signs or other safety-relevant data observed at screening, baseline, during the course of the trial and at the end-of-trial evaluation will be assessed with regard to possible changes compared to findings before start of treatment.

Relevant ECG findings will be reported as AEs.

7.3.4 Interim analyses

[figure not shown]
No interim analysis is planned.

7.3.5 Pharmacokinetic analyses

The pharmacokinetic parameters listed in [Section 5.5.1](#) for drug BI 1467335 will be calculated according to the relevant SOP of the Sponsor ([001-MCS-36-472](#)).

Subjects who are not included in the PKS (see [Section 7.3.1](#)) will be reported with their individual plasma concentrations and individual pharmacokinetic parameters. However, they will not be included in descriptive statistics or other statistical assessments for pharmacokinetic parameters.

Only concentration values within the validated concentration range and actual sampling times will be used for the calculation of pharmacokinetic parameters. Concentrations used in the pharmacokinetic calculations will be in the same format provided in the bioanalytical report, (i.e., to the same number of decimal places provided in the bioanalytical report).

7.4 HANDLING OF MISSING DATA

7.4.1 Safety

With respect to safety evaluations, it is not planned to impute missing values.

7.4.2 Plasma drug concentration - time profiles

Handling of missing PK data will be performed according to the relevant Corporate Procedure of the Sponsor ([001-MCS-36-472](#)).

Drug concentration data identified with NOS (no sample available), NOR (no valid result), NOA (not analysed), or BLQ (below the lower limit of quantification) will be displayed as such and not replaced by zero at any time point (this rule applies also to the lag phase, including pre-dose values).

7.4.3 Pharmacokinetic parameters

Handling of missing PK data will be performed according to the relevant SOP of the Sponsor ([001-MCS-36-472](#)). Missing PK parameters will not be imputed.

For the non-compartmental analysis, concentration data, identified as NOS, NOR or NOA will, in general, not be considered. Concentration values in the lag phase, identified as BLQ, will be set to zero. All other BLQ values of the profile will be ignored. The lag phase is defined as the period between time zero and the first time point with a concentration above the quantification limit.

7.5 RANDOMISATION

Subjects will be randomised to one of three treatment sequences in a 1:1:1 ratio. The block size will be documented in the CTR.

The sponsor will arrange for the randomisation as well as packaging and labelling of trial medication.

The randomisation list will be generated using a validated system which involves a pseudo-random number generator and a supplied seed number so that the resulting allocation is both reproducible and non-predictable.

The randomisation list will contain additional blocks to allow for subject replacement (see [Section 3.3.5](#)).

7.6 DETERMINATION OF SAMPLE SIZE

It is planned to include a total of 18 subjects in the trial because this sample size is considered sufficient to achieve the aims of this exploratory trial.

With this sample size, the below precision of the ratio of geometric means (test/reference) can be expected. Precision is defined as the ratio of upper to lower confidence interval limit.

Note that the precision is independent of the actual ratio of geometric means.

The observed geometric coefficient of variation (gCV) for BI 1467335 after single oral doses of 10 mg [REDACTED] BI 1467335 was 104% for AUC_{0-tz} and 94% for C_{max} [REDACTED] [REDACTED], [a href="c09036683">c09036683]. The reported variability listed in this trial (calculated from 6 individuals) originates from a parallel group design and is an estimate of the total variability and not of the between-subject variability. For a crossover study, an estimate of the intra-individual gCV is needed. Together with the correlation between two responses of the same subject ρ , we can estimate the intra-individual variability out of the total variability. A reasonable range for ρ in PK trials based on former experience is 0.6 to 0.7, where $\rho = 0.6$ is the conservative choice. [Table 7.6: 1](#) provides an overview of the resulting intra-individual gCVs.

Table 7.6: 1 Estimates of the intra-individual gCV

ρ	Endpoint	gCVT*	σ_T^2	σ_W^2	gCVw**
0.6	C_{\max}	94%	0.635	0.254	53.8%
	AUC_{0-tz}	104%	0.733	0.293	58.4%
0.7	C_{\max}	94%	0.635	0.190	45.8%
	AUC_{0-tz}	104%	0.733	0.220	49.6%

* gCV indicates the gCV for total variability.

** gCVw indicates the gCV for intra-individual variability

Assuming a gCV of 58.4% for AUC_{0-tz} of BI 1467335 and given the chosen sample size of 18 subjects, the precision of the two-sided 90% confidence interval of the gMean ratio will be approximately 2.09 (upper confidence limit/lower confidence limit); for a larger correlation of $\rho = 0.7$ and assumed intra-individual gCV of 49.6% for AUC_{0-tz} of BI 1467335, the precision would be approximately 1.89.

[Table 7.6: 2](#) provides an overview of the 90% confidence intervals that are expected with 95% probability, for possible scenarios of the ρ , gCV and intra-subject ratios (T/R).

Table 7.6: 2

Precision and expected two-sided 90% confidence intervals around the ratios of geometric means for different correlations (ρ) and ratios in a 3x3x3 cross-over trial (N=18)

ρ	PK parameter	Total gCV(%) ¹	Intra-indiv. gCV (%)	T/R (%)	90% CI (%)	Precision (Upper CL /Lower CL)
0.6	C _{max}	94%	53.8%	50	(36, 70)	1.98
				100	(71, 141)	1.98
				150	(107, 211)	1.98
	AUC _{0-tz}	104%	58.4%	50	(35, 72)	2.09
				100	(69, 144)	2.09
				150	(104, 217)	2.09
0.7	C _{max}	94%	45.8%	50	(37, 67)	1.81
				100	(74, 134)	1.81
				150	(112, 202)	1.81
	AUC _{0-tz}	104%	49.6%	50	(36, 69)	1.89
				100	(73, 137)	1.89
				150	(109, 206)	1.89

¹The total gCV in this table was calculated from individuals taken 10 mg [REDACTED] [c09036683])

All calculations were performed as described by Kupper and Hafner [[R12-0972](#)] using R Version 3.0.3.

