To this end, the PK endpoints will be log transformed (natural logarithm) prior to fitting the ANOVA model (see [Section 7.1.3](#)). For each endpoint, the difference between the expected means for $\log(T)-\log(R)$ will be estimated by the difference in the corresponding adjusted means (Least Squares Means), and a two-sided 90% confidence interval based on the t-distribution will be computed. These quantities will then be back-transformed to the original scale to provide the point estimate and 90% CIs for each endpoint.

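### Does the planned precision of 2.09 in protocol section 7.6 mislead, because it is a 95% limit whose variance comes from six subjects?

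*Protocol*

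**What the plan says.** Section 7.6 of the protocol justifies the sample size by precision alone: "It is planned to include a total of 18 subjects in the trial because this sample size is considered sufficient" for an exploratory trial. The measure is explicit: "Precision is defined as the ratio of upper to lower confidence interval limit".

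The variance input is a total gCV of 104% for AUC0-tz and 94% for Cmax from an earlier study, with its limits disclosed: "The reported variability listed in this trial (calculated from 6 individuals) originates from a parallel group design". The intra-individual part is obtained through an assumed correlation: "A reasonable range for ρ in PK trials based on former experience is 0.6 to 0.7", with 0.6 named as the cautious value.

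For AUC0-tz at a correlation of 0.6, the text says that "the precision of the two-sided 90% confidence interval of the gMean ratio will be approximately 2.09". That sentence opens by assuming a gCV of 58.4%. The next paragraph says that Table 7.6: 2 "provides an overview of the 90% confidence intervals that are expected with 95% probability" for stated scenarios. The note under the table names the Kupper-Hafner method.

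For the analysis itself, section 7.3.1 says that "a two-sided 90% confidence interval based on the t-distribution will be computed". Section 7.2 specifies no acceptance range and tests no hypothesis.

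**The concern.** Two things look wrong, and they pull in opposite directions.

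First, saying that the precision will be about 2.09 reads as a statement of the typical result. At the stated gCV and sample size, the typical ratio is nearer 1.84. On this reading, the section presents an upper limit as an expectation and makes the design look less precise than it is.

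Second, a 95% limit of this kind treats the within-subject variance as known. Here it was derived from a total variance estimated on six people, then split by an assumed correlation. Table 7.6: 2 varies the correlation but holds the total gCV at one value per endpoint, although the total gCV is the less certain of the two. On this reading, the design looks more precise than the source data can support.

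These figures are the only quantitative support for 18 subjects, and estimation is the trial's stated purpose. If they were wrong, readers would have a mistaken idea of how tightly the formulation ratio and the food effect will be known.

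**Working it through.** **Inputs**

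- N = 18, three periods, two-sided 90% interval (protocol 7.3.1, 7.6).
- Model with sequence, subject within sequence, period and treatment (7.1.3): 54 observations, so residual df = 54 − 1 − 17 − 2 − 2 = 32.
- t(0.95; 32) = 1.694; chi-square(0.95; 32) = 46.19.
- Intra-individual gCV from Table 7.6: 1, with σ_W² = ln(1 + gCV²). For AUC0-tz at a correlation of 0.6: ln(1 + 0.584²) = 0.2935.

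**Step 1: ratio at the assumed variance**

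Ratio = exp(2 · t · √(2σ_W²/N)). The standard error is √(2 × 0.2935/18) = 0.1806, so the exponent is 2 × 1.694 × 0.1806 = 0.612 and the ratio is 1.84. Simulation gave a mean of 1.84 and a median of 1.83.

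**Step 2: value not exceeded with 95% probability, variance known**

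The exponent is multiplied by √(46.19/32) = 1.2015: 0.612 × 1.2015 = 0.735, and exp(0.735) = 2.085. Conditioning on the interval covering the true ratio gives 2.09. The same steps for every scenario give:

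| Correlation | Endpoint | Ratio at assumed variance | 95% limit | Protocol |
|---|---|---|---|---|
| 0.6 | AUC0-tz | 1.84 | 2.085 | 2.09 |
| 0.7 | AUC0-tz | 1.70 | 1.89 | 1.89 |
| 0.6 | Cmax | 1.77 | 1.98 | 1.98 |
| 0.7 | Cmax | 1.64 | 1.81 | 1.81 |

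At a true ratio of 100%, the AUC0-tz interval at a correlation of 0.6 is 100/√2.085 to 100 × √2.085, or 69 to 144%, as tabulated. The protocol's figures are therefore correct 95% limits. With the variance known, the chance of a ratio at or below 2.09 is 0.953.

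**Step 3: the six-subject uncertainty carried through**

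Assumptions: one group of six (5 df), log-normal data, correlation exactly 0.6, 18 completers. A ratio of 2.09 corresponds to an observed residual variance of (ln 2.09/(2 × 1.694))² × 18/2 = 0.426. Divided by 0.293 this is 1.454. The observed variance relative to the planning estimate then follows F(32, 5), and P(F ≤ 1.454) = 0.636.

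On the same basis the median ratio is 1.91, the 80% point 2.45, the 90% point 2.97 and the 95% point 3.65. The last is an interval of about 52 to 191% at a true ratio of 100%.

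**Step 4: how firm is the 64%?**

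Still on 5 df, it is 52% if the true correlation is 0.5, 70% at 0.65 and 76% at 0.7. With 15 completers at 0.6 it is about 54%. The 95% confidence interval for the total variance of 0.733 is 0.29 to 4.41. Put through the protocol's own method at a correlation of 0.6, these ends give precisions of 1.58 and 6.06, so the uncertainty runs in both directions.

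**The case for a change.** The strongest case for a change is that interval width is this design's only operating characteristic, and the section's sensitivity analysis varies the wrong input. Moving the correlation from 0.6 to 0.7 takes AUC0-tz precision from 2.09 to 1.89. Moving the total variance to its one-sided 80% upper limit (0.733 × 5/2.343 = 1.56, a total gCV of about 194%) takes it to 2.93 by the protocol's own method. Describing 0.6 as the cautious choice covers only the correlation. The remedy would cost a sentence and a table row.

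Much of this stands as description. The wording around 2.09 is loose, no sensitivity to the total gCV is shown, and the figures above are correctly computed. The claim that 2.09 is not a true 95% limit does not stand. The protocol gives the limit for an assumed gCV, and on that condition it is right. The 64% answers a different question, a predictive one that section 7.6 does not claim to address, and it too depends on fixing an uncertain input, the correlation.

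**Conclusion.** No change is needed. What remains is a matter of wording: a 95% limit (2.09 for AUC0-tz, 1.98 for Cmax, at a correlation of 0.6) is described in language that suits the ratio at the assumed variance (1.84 and 1.77). A reader of the whole section can resolve this, because the 95% probability, the method, the assumed gCV and the six-subject source are all stated there. Read as a typical result, 2.09 errs on the cautious side; even with the 5-df uncertainty included, the median is 1.91.

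Conditioning a planning figure on an assumed variability is an ordinary and disclosed choice. There is no precision target or acceptance range for the design to miss. The 90% intervals in the report will come from the trial's own residual error, so a planning gCV that proves wrong cannot make the results look tighter than they are. Relabelling the figure or adding a sensitivity row would leave the 18 subjects, the model, the reported intervals and the conclusions unchanged.

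The reproduced limits rest on 18 completers and 32 residual df. The 64% additionally needs log-normal data, 5 df and a correlation of 0.6, and ranges from about 52% to 76% for true correlations of 0.5 to 0.7.

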8. INFORMED CONSENT, DATA PROTECTION, TRIAL RECORDS

The trial will be carried out in compliance with the protocol, the principles laid down in the Declaration of Helsinki, in accordance with the ICH Harmonised Tripartite Guideline for Good Clinical Practice (GCP) and relevant BI SOPs.

The investigator should inform the sponsor immediately of any urgent safety measures taken to protect study subjects against any immediate hazard, and also of any serious breaches of the protocol or of ICH GCP.

As a general rule, no trial results should be published prior to finalisation of the CTR.

Insurance Coverage: Terms and conditions of the insurance coverage must be given to each subject and are made available to the investigator via documentation in the ISF.

8.1 STUDY APPROVAL, SUBJECT INFORMATION, AND INFORMED CONSENT

This trial will be initiated only after all required legal documentation has been reviewed and approved by the respective Institutional Review Board (IRB) / Independent Ethics Committee (IEC) and competent authority (CA) according to national and international regulations. The same applies to the implementation of changes introduced by amendments.

Prior to a subject's participation in the trial, written informed consent must be obtained from each subject (or the subject's legally accepted representative) according to ICH GCP, and regulatory and legal requirements of the participating country. Each signature must be personally dated by each signatory, and the informed consent and any additional subject information form is to be retained by the investigator as part of the trial record. A copy of the signed and dated written informed consent and any additional subject information must be given to each subject or the subject's legally accepted representative.

The subject must be informed that his personal trial-related data will be used by Boehringer Ingelheim in accordance with the local data protection laws. The level of disclosure must also be explained to the subject.

The subject must be informed that his medical records may be examined by authorised monitors (CML/CRA) or Clinical Quality Assurance auditors appointed by Boehringer Ingelheim, by appropriate IRB/IEC members, and by inspectors from regulatory authorities.

8.2 DATA QUALITY ASSURANCE

A quality assurance audit/inspection of this trial may be conducted by the sponsor or sponsor's designees, by IRBs/IECs, or by regulatory authorities. The quality assurance auditor will have access to all medical records, the investigator's trial-related files and correspondence, and the informed consent documentation of this clinical trial.

Data management procedures to ensure the quality of data are described in detail in the trial data management and analysis plan (TDMAP) available in the TMF.

8.3 RECORDS

CRFs for individual subjects will be provided by the sponsor. For drug accountability, refer to [Section 4.1.8](#).

[REDACTED]

8.3.1 Source documents

Source documents provide evidence for the existence of the subject and substantiate the integrity of the collected data. Source documents are filed at the investigator's site.

All data reported in the CRFs must be consistent with source data or discrepancies must be explained.

[REDACTED]

The investigator may need to request previous medical records or transfer records, depending on the trial.

8.3.2 Direct access to source data and documents

The investigator/institution will permit trial-related monitoring, audits, IRB/IEC review and regulatory inspection, providing direct access to all related source data/documents. CRFs and all source documents, including progress notes (if applicable) and copies of laboratory and medical test results must be available at all times for review by the sponsor's clinical trial monitor, auditor and inspection by health authorities (e.g. FDA). The Clinical Research Associate (CRA)/on site monitor and auditor may review all CRFs, and written informed consents. The accuracy of the data will be verified by reviewing the documents described in [Section 8.3.1](#).

8.3.3 Storage period of records

Trial site:

The trial site must retain the source and essential documents (including ISF) according to the national or local requirements (whatever is longer) valid at the time of the end of the trial.

Sponsor:

The sponsor must retain the essential documents according to the sponsor's SOPs.

8.4 EXPEDITED REPORTING OF ADVERSE EVENTS

BI is responsible to fulfil their legal regulatory reporting obligation and in accordance to the requirements defined in this CTP.

8.6 COMPLETION OF TRIAL

The IEC / competent authority of the EU member state needs to be notified about the end of the trial (last subject / subject out, unless specified differently in [Section 6.2.3](#) of the CTP) or early termination of the trial.

10. APPENDICES

10.1 RECONSTITUTION INSTRUCTION

10.1.1 Drug supplies overview

- a) BI 1467335 Powder for Oral Solution 40 mg (target solution concentration BI 1467335: 0.5 mg/mL), provided in 100 mL brown glass bottles with screw cap
- b) Solvent for Oral Solution 80 mL (███████████) provided in 100 mL glass vials with tear-off caps

10.1.2 Required equipment and dosing aids - overview

- a) Mechanical (orbital) shaker for bottles (e.g. Bühler Type KL2)
- b) Dosing dispensers/syringes and bottle adapters

For the withdrawal of respective volume aliquots from the final oral solution to be administered, amber oral dispensers/ syringes (e.g. BAXA/ BAXTER ExactaMed) should be used in a size as close as possible to the required dose volume. For this purpose a range of syringe sizes from 1 mL up to 60 mL should be stocked at the trial site. In order to ease the withdrawal of the oral solution from glass bottles with the above syringes, bottle adapters (e.g. BAXA/ BAXTER AdaptaCap, Bottle Adapters (E-28 mm), Order No. H9385105) and dispenser tip caps (e.g. Order No 50300) should be used and stocked in the trial sites.

Possible amber BAXA ExactaMed dispensers/ syringes

- BAXA ExactaMed amber oral dispenser 1 mL – e.g. Order No – 1601*
- BAXA ExactaMed amber oral dispenser 3 mL – e.g. Order No – 1602*
- BAXA ExactaMed amber oral dispenser 5 mL – e.g. Order No – 1605*
- BAXA ExactaMed amber oral dispenser 10 mL – e.g. Order No – 1610*
- BAXA ExactaMed amber oral dispenser 20 mL – e.g. Order No – 1620*
- BAXA ExactaMed amber oral dispenser 35 mL – e.g. Order No – 1635*
- BAXA ExactaMed amber oral dispenser 60 mL – e.g. Order No – 1650*

* ... or corresponding BAXTER Order-No

Only CE certified syringes are to be used!

10.1.3 Reconstitution procedure

2 bottle concept, see also [Section 10.1.4](#).

[figure not shown]
Proprietary confidential information © 2016 Boehringer Ingelheim International GmbH or one or more of its affiliated companies

Step 2: Open the vial containing the solvent for oral solution

The final BI 1467335 oral solution concentration is 0.5 mg/mL.

10.1.4 Illustration of reconstitution procedure

The following scheme on the principle followed for the present PfoS formulation, 2-bottle concept, should serve as an additional illustration to clarify, how the reconstitution has to be performed.

Proprietary confidential information © 2016 Boehringer Ingelheim International GmbH or one or more of its affiliated companies

The following picture shows an example of the powder and solvent bottles needed for the preparation of the final oral solution for administration.

10.1.5 In-use stability

The in-use stability of the reconstituted solution is [REDACTED] after its preparation, incl. storage in BAXA dispensers/syringes until administration. Therefore, it must be prepared in the morning of the administration. Further details are given on the CTS labels.

10.1.6 Mode of application

Withdraw the required volume aliquot with amber dispensers/syringes (e.g. BAXA/BAXTER ExactaMed) to obtain the required doses. If the complete content of a bottle is to be used, it can be administered directly out of the bottle. Use syringes at a volume size as close as possible to the volume to be withdrawn.

Please note that it is the responsibility of the investigator to assure that appropriate supplies are used for administration of a dose, based on guidance in the clinical trial protocol, and dosing is limited to the allowed dosing range for a specific dose formulation as stated in this Reconstitution Instruction.

Proprietary confidential information © 2016 Boehringer Ingelheim International GmbH or one or more of its affiliated companies

